Aim 1. Maximize exercise-mediated recovery of limb muscles by using stimulation induced spinal plasticity. We will study the effect of limb training combined with Spike-Timing Dependent Plasticity (STDP) on motor function recovery. We will test the effect of three groups: (1) stimulation, (2) training +stimulation, and (3) training+sham stimulation. We hypothesize that the ability of training to promote recovery of limb motor function will be enhanced by eliciting STDP in upper and lower-limb. An important strength of this aim is the combination of training and STDP, which aims at enhancing the beneficial effects of motor training by promoting plasticity in the corticospinal pathway (Ellaway et al., 2007; Castel et al., 2009). Training effects on physiological pathways will be explored and correlated with hand/arm motor function and the site and extent of the lesion defined by structural MRI.

Aim 2. Maximize exercise-mediated recovery of limb muscles by using stimulation induced spinal plasticity. STDP has been shown to be effective in enhancing the recovery of residual limb function in humans with chronic incomplete SCI (Urbin et al., 2017). In this aim we will investigate the effect of the combination of extended STDP and training. We hypothesize the ability of training to promote recovery of motor function will be enhanced by eliciting STDP in the corticospinal pathway.

BACKGROUND:

After a SCI, many individuals present deficits in upper-limb and/or lower-limb function. Most SCIs are contusions and ~50% occur at the cervical level causing anatomically incomplete damage and bilaterally functional deficits to lower- and upper-limbs (Kakulas, 1999). Arm and leg function deficits limit daily-life activities, such as reaching and grasping, eating, writing, and walking which decreases the quality of life (Snoek et al., 2004). Regaining arm and leg function is considered the highest priority for improving the quality of life of individuals with SCI (Anderson, 2004).

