Rehabilitation strategies in humans with SCI rely on the use of exercise (Harkema et al., 2012; Behrman et al., 2017). Exercise training aims to drive neural networks in an activity-dependent manner to elicit plasticity and facilitate functionally relevant muscle activity below the level of injury (Knikou, 2010). Studies using animals (Courtine et al., 2009; Hill et al., 2009; McPherson et al., 2015) and humans (Rejc et al., 2017; Gad et al., 2018; Gill et al., 2018) agree that physiological and functional effects of exercise can be augmented by the use of neural stimulation, which is thought to increase the likelihood of activating spared neural pathways. Even though these approaches have facilitated exercise-mediated recovery, the overall effects remain limited. Clearly, there is a need to develop interventions that can more effectively engage spared neural connections to further improve functional recovery due to rehabilitative exercise in humans with SCI.

Evidence has shown that corticospinal transmission can be enhanced by precisely timing pairs of presynaptic and postsynaptic action potentials arriving at the spinal cord (Taylor & Martin, 2009),

which can enhance voluntary motor output in humans with (Bunday and Perez, 2012) and without (Taylor & Martin 2009) SCI. Evidence has shown that the activity in upper-limb muscles can be enhanced by activations of the lower limb (Zhou et al., 2017). Therefore a strategy that combine upper and lower limb stimulation and activity might be more effective to enhance upper limb function. In this protocol, we will test the effect of training combined with stimulation to facilitate upper and lower limb function.

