How STDP and training might contribute to recovery of upper-limb and lower-limb function: The physiological basis for these protocols comes from animal studies showing that an increase or decrease in synaptic strength can be elicited by repeated pairs of presynaptic and postsynaptic action potentials that are precisely timed with respect to each other (Bi & Poo, 1998; Dan & Poo, 1998; Bi & Poo, 2001). If antidromic stimulation of a postsynaptic cell is paired with timed orthodromic stimulation of a presynaptic cell, bidirectional plasticity can be induced (Bi & Poo, 1998; Markram et al., 1997). In humans, corticospinal neurons can be activated by transcranial magnetic stimulation (TMS), and antidromic action potentials can be elicited in sensorimotor cortex and motoneurons by peripheral nerve/ spinal cord stimulation. STDP has been used successfully to precisely pair pulses to arrive at the spinal cord (Taylor & Martin, 2009). How to strengthen synaptic plasticity in corticospinal connections targeting the spinal cord (spinal synapses) of upper-limb and lower-limb muscles after SCI combined with training and its effect on voluntary output, remains unknown and will be investigated in this study.

STUDY ENDPOINTS:

The primary outcome measure utilized in this part of study is the Graded Redefined Assessment of Strength, Sensibility and Prehension (GRASSP see below). GRASSP is an extensive and validated impairment and functional measure which is able to detect subtle neurologic changes in individuals with spinal cord injury. Specifically, it evaluates the domains of sensation, strength, quality of different grip patterns and the ability to complete a variety of functional tasks.

The primary outcome measure utilized in this part of study the 10-meter Walk test. In the group receiving lower-limb exercises, we will use the 10-meter walk test to assess walking speed in meters per second. The same percentage of body-weight support will be used during pre- and post-assessments. A stopwatch will be used to measure the time to execute the task. The 10-meter walk will be repeated 3 times and the average will be used.

Participants may complete the following secondary endpoint measurements before and after the STDP protocol as outlined below.

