All participants will exercise immediately after the stimulation paradigm. Upper-limb exercises will involve gross grasping, fine grasping, and hand cycle using an arm ergometer. During gross grasping, subjects will be asked to reach and grasp cylinders, blocks, cups and lids randomly presented on a table located in front of them at a height of ~20 cm. Then, subjects will be asked to reach and grasp the object to put it back on the table. These sets of movements will be repeated 20 times for each object with breaks as needed. During fine grasping, participants will perform similar movements but they will be asked to reach and grasp smaller objects (peg, bead, pinch pin, cube). During hand cycle, the arm ergometer will be used for 15 minutes and grasping gloves will be used as needed. Movements will be passive, active-assisted, or active depending on participant's ability to perform tasks. In addition, training will consist of grasping with the thumb and index finger targets of different diameters (1, 2.5, and 6 cm) in a vertical board (36x30") positioned in front of them. The board will contain 6 panels (12x15") which will light up individually by a computer cue. Each panel will have three LED lights to indicate grip strength to be exerted (red=30% MVC, blue=20% MVC, yellow=5% MVC). A reflective line in each target will identify the place to grasp, which will be modified to increase task difficulty. Force transducers will run along the sides of each target to communicate with LEDs. Kinematics and EMG signals will be acquired through surface electrodes. Subjects will be instructed to grasp the object between index finger and thumb as fast and accurately as possible holding the final posture for 3 s until the light disappear. 300 trials will be completed.

Lower Limb Training

All participants exercised immediately after STDP or sham-STDP. Lower-limb exercises will involve over-ground walking, treadmill walking, and stair climbing training. During locomotor training, subjects will use a body-weight support system with ~0-70% of body weight support. During treadmill training, subjects will walk at a speed of 0.1-0.3 m/s for 10 minutes using the body-weight support system.

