If eligible, participants will be asked to complete pre, post, and follow-up assessment sessions in addition to the training sessions. Each assessment will require 2-5 sessions. Participants will complete up to 135 training sessions with a maximum of 360 paired pulses of stimulation and a small cohort of participants (n=10) will complete up to 270 training sessions with a maximum of 720 paired pulse of stimulation (up to 4 times per day). This will be determined based on preliminary data. In Aim 1, participants will be tested before and after at least 10 training sessions with single site stimulation. In Aim 2, participants will be tested before and after at least 40 training sessions with multisite stimulation. If a training session is not completed or missed participants will be asked to recover that session in a timely manner.

AIM 1: Randomized controlled design

Pre-assessment: 1. Physiology 2. Kinematics 3. Function	Stimulation Training + stimulation Training + sham stimulation	Post-assessment: 1. Physiology 2. Kinematics 3. Function	Follow-up assessment: 1. Physiology 2. Kinematics 3. Function
--	--	---	--

AIM 2:

Pre-assessment: 1. Physiology 2. Kinematics 3. Function	Training + stimulation	Post-assessment: 1. Physiology 2. Kinematics 3. Function	Follow-up assessment: 1. Physiology 2. Kinematics 3. Function
--	------------------------	---	--

We anticipate that each participant will take about 2-10 months to complete the study procedures/testing. Follow-up assessments will be done 1-9 months after completion of protocol, one follow-up in the first 3 months and the last follow-up in the 4-9 months following the last completed session. We will evaluate the subject's ability to move their hands, arms, legs, feet and/or toes using the different physiological and functional tests as mentioned above. TMS measurements, CMEPS and EMG recordings may also be done at these follow-up assessments.

INCLUSION AND EXCLUSION CRITERIA:

We anticipate the screening of 500 subjects across the two aims (60 subjects for Aim 1, and 40 for Aim 2) who have incomplete SCI at the cervical/thoracic/lumbar level (C2-L2). This number accounts for an attrition rate of 50%. To account for screen failures we would like to ask for a total of 200 subjects.

- Inclusion criteria for SCI subjects:
 - (1) Male and females between ages 18-85 years
 - (2) SCI at least 4 weeks post injury
 - (3) Spinal Cord injury at or above L2
 - (4) ASIA A,B,C, or D, complete or incomplete

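### GRASSP and the 10-meter walk are each called primary but neither is assigned to an aim; the limb studied in Aim 1 is contradictory, and its 45 is tied to no endpoint or limb

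*Combined protocol and SAP*

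**What the plan says.** All references are to the combined protocol and SAP.

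- **STUDY ENDPOINTS** opens with "The primary outcome measure utilized in this part of study is the Graded Redefined Assessment of Strength, Sensibility and Prehension". The next paragraph calls the 10-meter walk the primary outcome in the same terms and adds "In the group receiving lower-limb exercises, we will use the 10-meter walk test to assess walking speed in meters per second". The parts of the study are not defined, and neither paragraph names an aim.
- **OBJECTIVES, Aim 1** has three arms: stimulation, training plus stimulation, and training plus sham. Its hypothesis is that training-related "recovery of limb motor function will be enhanced by eliciting STDP in upper and lower-limb". The same paragraph plans to correlate training effects with hand and arm function.
- **OBJECTIVES, Aim 2** states "We hypothesize the ability of training to promote recovery of motor function will be enhanced by eliciting STDP in the corticospinal pathway". No limb is named.
- **BACKGROUND** suggests that "a strategy that combine upper and lower limb stimulation and activity might be more effective to enhance upper limb function".
- **Upper limb training** begins "All participants will exercise immediately after the stimulation paradigm". **Lower Limb Training** begins "All participants exercised immediately after STDP or sham-STDP".
- **STUDY TIMELINE** separates the aims by number of sessions and by single-site versus multisite stimulation: "In Aim 2, participants will be tested before and after at least 40 training sessions with multisite stimulation". It shows Aim 1 as randomised with three arms and Aim 2 as one training plus stimulation arm.
- **INCLUSION AND EXCLUSION CRITERIA** asks for grip and/or wrist ability in Aim 1, and for dorsiflexion and hip-flexor contraction in Aim 2. It gives 60 subjects for Aim 1 and 40 for Aim 2, and mentions 50% attrition.
- **Statistical Analysis** gives 45 (15 per group) for Aim 1 and 11 for Aim 2, each at alpha 0.05 and power 0.8, for physiological and behavioral outcomes in general.

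**The concern.** A reader cannot tell from the plan which primary outcome is analysed in which aim, in which participants and in which arms. This is more than missing detail, because the sections disagree. The ability criteria point to an upper-limb Aim 1. Aim 1's own hypothesis and the sham wording under lower-limb training point to lower-limb participants in Aim 1 as well.

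The analysis set, the power and the error rate all depend on the answer. Left open, the choice could be made after results are seen. A second problem sits beside it: the Aim 2 hypothesis is comparative, but its design has no comparator.

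**Working it through.** **1. Which primary belongs to which aim?**

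| Evidence | Points to |
|---|---|
| Ability criteria: hand/wrist for Aim 1, leg for Aim 2 | GRASSP in Aim 1, walk in Aim 2 |
| Aim 1 correlates effects with hand and arm function | GRASSP in Aim 1 |
| The study cited for Aim 2 has a lower-limb title in the Bibliography | walk in Aim 2 |
| Aim 1 hypothesis covers both limbs | both in Aim 1 |
| Lower-limb training follows real or sham stimulation; sham exists only in Aim 1 | walk also in Aim 1 |
| STUDY TIMELINE separates the aims by sessions and stimulation sites | does not settle it |

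The first three rows make one primary per aim the best-supported reading. The next two contradict it.

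**2. Can the 45 be reproduced?** No. The documents give no effect size, SD, within-subject correlation or endpoint. The available check is to solve for the effect that gives 80% power at 15 per group and alpha 0.05, then hold it fixed.

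- One-way F on change, 3 groups: noncentrality λ = f²N with 2 and N − 3 degrees of freedom. At N = 45, power 0.80 requires f = 0.480.
- GROUP x TIME interaction, 3 groups, m = 4 times, sphericity: λ = f²Nm/(1 − ρ) with 6 and 3(N − 3) degrees of freedom. At N = 45 and assumed ρ = 0.5, power 0.80 requires f = 0.199. The powers below are the same at ρ = 0.3 or 0.7 once f is recalibrated.

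Many designs fit 45, so the number does not identify an endpoint.

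**3. Illustration if Aim 1 has separate limb groups.** The same effects, with an even split by limb (assumed):

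| Basis | Per group per limb | One-way F | GROUP x TIME |
|---|---|---|---|
| 15 per group is per limb | 15 | 0.80 | 0.80 |
| 45/(3 x 2) = 7.5 | 7 | 0.424 | 0.401 |
| 45/(3 x 2) = 7.5 | 8 | 0.485 | 0.463 |
| 60 enrolled, 50% lost: 30/(3 x 2) | 5 | 0.292 | 0.273 |

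The last row is one way to read the attrition sentence, which does not say clearly which number it adjusts.

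**4. Illustration if the same people contribute both primaries.** Each is tested at 0.05, either counts as success (assumed), and there is no true effect. If the endpoints are independent, the familywise error is 1 − 0.95² = 0.0975. Simulation (100,000 runs, one-way F, 15 per group) gives about 0.096 at endpoint correlation 0, 0.092 at 0.5 and 0.072 at 0.9. The range is about 7-10%.

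**5. Aim 2.** Everyone receives training plus stimulation. The pre-post change therefore combines the effect of training, any added effect of stimulation, and change over time. The hypothesis concerns the second component alone, and one arm cannot isolate it at any sample size.

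**The case against.** The strongest reply is that the plan already implies one primary per aim. STUDY ENDPOINTS separates the outcomes by part of the study and confines the walk to a lower-limb group, and the ability criteria pair the hand with Aim 1 and the leg with Aim 2. On that reading there is no split sample and no second primary within an aim. This stands as the best-supported reading, but not as a settled one, because the Aim 1 hypothesis and the sham wording under Lower Limb Training contradict it.

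Some stronger inferences are tempting and should not be drawn.

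- **That Aim 1 is underpowered at 40-49%.** This needs an even split of the 45, which the plan does not state. The 15 per group could be per limb.
- **That the trial has a 7-10% false-positive rate.** This needs both primaries in the same people and a rule that either suffices. Support for the same people training both limbs is thin. The BACKGROUND sentence is rationale. The two statements about all participants each sit under a separate training heading; read literally, they would also have the stimulation-only arm exercising.
- **That someone without leg movement would enter an Aim 1 walk comparison.** This cannot happen if Aim 1 is upper limb only.
- **That Aim 2 lacks a comparator because the endpoints are unassigned.** It lacks one under every reading, so this is a separate fault.

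**Conclusion.** The point holds as an internal contradiction about which primary, limb and arms belong to each aim, together with an Aim 1 sample size attached to no endpoint or limb. It should be resolved before analysis. Confidence is medium, because one reading is better supported than the others.

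The size is conditional. For Aim 1 it runs from no loss of power (upper limb only, or 15 per group per limb) through about 40-49% (even split of the 45) to about 27-29% (60 enrolled, even split, half lost). Each figure assumes that 15 per group gives 80%. The 7-10% error rate applies only under the assumptions in step 4 of the working. None of these figures is a property of the plan as written.

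The Aim 2 conclusion needs no such assumption: its single arm supports a statement about change within the group, not one about enhancement by stimulation.

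**What to change.** Reconcile OBJECTIVES, STUDY ENDPOINTS, the two training sections, STUDY TIMELINE, the ability criteria and Statistical Analysis. State for each aim the target limb, the one primary outcome and the arms in which it is measured. Then, according to what was intended:

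- **Aim 1 is upper limb only.** Say so in the Aim 1 hypothesis and in the training sections, and make GRASSP its primary.
- **Aim 1 has separate limb groups.** Stratify randomisation by target limb, and reconcile the entry ability criterion with the limb studied. State whether the walk test is also measured in the stimulation-only arm, since STUDY ENDPOINTS confines it to those receiving lower-limb exercises. State how a walk that cannot be completed is scored. Say whether 15 per group is per limb; if it is not, restate power per limb or make one endpoint secondary.
- **The same people contribute both measures.** Name one primary or state a multiplicity rule.

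In every case, report Aim 2 as a within-group pre-post change and not as evidence that stimulation enhances training.

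The cost is protocol and SAP wording, plus a stratified randomisation list only if the limbs are separate groups. The downside is a less favourable stated power, or one endpoint becoming secondary. No extra enrolment is proposed.

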amplitude of the non-rectified response in control subjects and both legs of individuals with and without spasticity as determined by the MAS. Soleus H-reflex and M-max: Participants will be comfortably seated in an armchair. Percutaneous electrical stimulation of the posterior tibial nerve will be delivered (using 1 ms rectangular electrical stimulus, DS7AH, Digitimer) through a cathode (10mm diameter Ag-AgCl electrode) placed in the popliteal fossa over the posterior tibial nerve and an anode (Ag-AgCl plaque) placed over superior to the patella. Stimulus intensities will be increased in steps of 0.05 mA, starting below H-reflex threshold and increasing up to measure the H-max and Mmax at rest (0.25 Hz). The H-max and M-max will be measured as peak-to-peak amplitude of the non-rectified response in control subjects and both legs of individuals with and without spasticity as determined by the MAS.

E) EMG and force voluntary output: Individuals will perform a maximum voluntary contraction (MVC) of the targeted muscles (deltoid, biceps brachii, first dorsal interosseous, abductor pollicis brevis, quadriceps femoris, tibialis anterior and/or soleus) through surface electrodes secured to the skin over the belly of each muscle (Ag-AgCl, 10 mm diameter). The signals will be amplified, filtered (20–1000 Hz), and sampled at 10 kHz for offline analysis.

F) Nine Hole Peg Test (9HPT): This test measures finger dexterity. The board is placed at the participant's midline, with the container holding the pegs facing toward the hand being tested. Nine small pegs are placed in a container and subjects are instructed to pick up each of the pegs and put them back as fast and accurately as possible. The time to complete the task is measured in seconds.

G). Jebsen Taylor Test (JTT): This test measures hand function. The time in seconds to complete subcomponents of the JTT will be measured for both hands.

H) Chedoke Arm and Hand inventory (CAHAI): This test measures upper-limb motor recovery. Quantitative scale with 13 items (each item is given a score: 1 to 7).

I) Electrical Perceptual Threshold (EPT): This test provides a quantitative measure of sensory function by using small pulses of electricity on the surface of the skin and will be used to evaluate sensory threshold in the hands/arms and legs.

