J) Kinematics: These will be measured during self-paced and fast grasping or walking movements recorded by OptiTrack V100 cameras (120 Hz) and by Opti Track, V120: Trio camera, NaturalPoint, Inc., with cameras respectively for the locomotor training. Subjects will be seated and grasp with the less affected (participants) and dominant (controls) arm. Cameras will be positioned in front/sides of subjects with markers on the tip of the thumb and index finger, inner side of the wrist, lateral side of the elbow and shoulder joints. Variables: 1) Movement onset (MO): time between the GO signal and start of forward arm velocity. 2) Total movement duration (MD): time between MO and grasp (Gr=time when index and thumb contact target). MD will be broken in

time to reach maximum velocity (MV), maximum hand aperture (MA), and the first finger contact (FC), and Gr.

K) Startle: We will test the StartReact response to assess contributions from the reticulospinal tract. Participants will be asked to observe a red LED located ~1 m in front of them. When the LED is illuminated, individuals will be asked to perform as fast as possible isometric muscle contractions. In some trials, the LED will be presented with a quiet (<95 dB; 50 ms) or a startling (SAS, >115 dB; 50 ms) acoustic stimulus. We will measure: (a) visual reaction time (defined as the onset of the EMG burst in the contracted muscle after the LED), (b) auditory reaction time (time delay between the presentation of the quiet acoustic stimulus and the onset of the EMG response), and (c) visual+startle reaction time (time between the SAS and the EMG onset).

L) Pendulum Test: As part of the physical exam, we will use the pendulum test to measure muscle tone at the knee by using gravity to provoke muscle stretch reflexes during passive swinging of the lower limb.

M) Portable Spasticity Assessment Device (PSAD): The PSAD combine biomechanical and electrophysiological measurements for an objective quantification of active and passive component of muscle stiffness (Lorentzen et al., 2017). The device functions as a dynamometer integrating measurement of force, joint movement, and reflex-mediated muscle activity.

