 - (5) Possess the following abilities
 - (Aim 1) The ability to produce a visible precision grip force with one hand, and/or the ability to perform some small wrist flexion and extension (Aim 2) The ability to perform a small visible contraction with dorsiflexion and hip flexor muscles

- Exclusion criteria for SCI Subjects:
 - (1) Uncontrolled medical problems including pulmonary, cardiovascular or orthopedic disease
 - (2) Any debilitating disease prior to the SCI that caused exercise intolerance
 - (3) Premorbid, ongoing major depression or psychosis, altered cognitive status
 - (4) History of head injury or stroke
 - (5) Vascular, traumatic, tumoral, infectious, or metabolic lesion of the brain, even without history of seizure, and without anticonvulsant medication
 - (6) History of seizures or epilepsy
 - (7) Receiving drugs acting primarily on the central nervous system, which lower the seizure threshold (see appendix 2)
 - (8) Pregnant females
 - (9) Ongoing cord compression or a syrinx in the spinal cord or who suffer from a spinal cord disease such as spinal stenosis, spina bifida, MS, or herniated disk
 - (10) Metal plate in skull
 - (11) Individuals with scalp shrapnel, cochlear implants, or aneurysm clips

RECRUITMENT METHODS:

We anticipate screening of 500 subjects to complete the study (see description above). We will be using the IRB approved SCI registry for recruitment. A letter granting access to the registry is included in the submission. Subjects who have previously expressed an interest in participating in research studies at the Shirley Ryan AbilityLab complete a questionnaire and request that their information be entered into the research volunteer database. This database is searchable based on criteria such as age, time-post injury and injury level. Potential subjects will be called by the study coordinator. If the individuals have not agreed to be contacted by phone for future studies then the treating physician will be the one contacting them. The phone call will be to provide information about the study to the individual to determine if they are interested in the study. We will not be collecting any information from the individual. All the screening will be done after written consent is collected and before enrollment.

COMPENSATION FOR PARTICIPATION IN RESEARCH ACTIVITIES:

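### The timed hand tests (9HPT, JTT, grasp duration) have no score for a participant who cannot complete them, so a gain from unable to able is not credited on these secondary outcomes

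*Combined protocol and SAP*

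**What the plan says.** In STUDY ENDPOINTS, three hand measures are defined only by the time at which a task is finished:

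- Item F, Nine Hole Peg Test (9HPT): "The time to complete the task is measured in seconds". The protocol does not say which hand or hands are analysed.
- Item G, Jebsen Taylor Test (JTT): "The time in seconds to complete subcomponents of the JTT will be measured for both hands".
- Item J, kinematics: total movement duration is the "time between MO and grasp (Gr=time when index and thumb contact target"). Participants "grasp with the less affected (participants) and dominant (controls) arm".

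None of these items gives a maximum time, a score for a test that cannot be completed, or a count of items finished. Their status is set at the head of the list: "Participants may complete the following secondary endpoint measurements before and after the STDP protocol as outlined below".

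In INCLUSION AND EXCLUSION CRITERIA, criterion 4 admits "ASIA A,B,C, or D, complete or incomplete". Criterion 5 for Aim 1 asks for "The ability to produce a visible precision grip force with one hand, and/or the ability to perform some small wrist flexion and extension". Wrist movement without grip is therefore enough.

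Statistical Analysis, Aim 1, names a repeated-measures ANOVA with Tukey comparisons over three groups and four time points for all behavioral outcomes, with 15 participants per group. It has no rule for a test that is missing or could not be performed.

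**The concern.** A completion time exists only if the task is completed. The entry rule admits people who may be unable to place nine pegs, finish some JTT subcomponents or bring thumb and index finger onto a target. The upper-limb training section foresees limited ability, since it allows movements to be passive or assisted, but the scoring does not.

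Two things follow. A participant with no baseline time who can do the test afterwards has no change score, so the kind of recovery that Aim 1 looks for is not credited on these tests. Also, whether a time exists after treatment depends on treatment, so the set with usable times can differ between randomised arms. With 15 per group, a few such people matter. If the choice between dropping them, assigning a ceiling and imputing is made after the data are seen, the result can depend on that choice.

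**Working it through.** **Plan's own figure.** Aim 1 states 45 participants (15 per group) for alpha 0.05 and power 0.80, without an effect size, SD or correlation, so 45 can be neither reproduced nor refuted. Solving backwards for one pairwise comparison, two-sided:

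d = (1.960 + 0.842) × √(2/15) = 2.802 × 0.365 = 1.02 (normal approximation), or 1.06 with the t-test.

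**Check 1: smaller sample only.** Assume a share u has no baseline time and is left out. Power = Φ(d√(n/2) − 1.96) with d = 1.02 (1.023 before rounding) and no Tukey adjustment. The range of u is assumed, because the documents give none.

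| u | n per arm | d√(n/2) − 1.96 | Power |
|---|---|---|---|
| 10% | 14 | 0.75 | 0.77 |
| 20% | 12 | 0.55 | 0.71 |
| 30% | 10 | 0.33 | 0.63 |
| 40% | 9 | 0.21 | 0.58 |

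**Check 2: inability at either visit.** Assumed model: two arms of 15; ability standard normal; pre-post correlation 0.8, so the SD of change is √(2 × 0.2) = 0.632; treated arm shifted by 1.06 × 0.632 = 0.67. Speed is ability minus a threshold, and 0 below it. The threshold is set so that u cannot do the test at baseline. Both analyses are t-tests on change in speed, so only the handling of unable participants differs. Power is simulated and good to a point or two.

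| u | Retained, control / treated | Newly able, treated | Power, completers only | Power, all with 0 for unable |
|---|---|---|---|---|
| 10% | 86% / 90% | 8% | 73% | 80% |
| 20% | 73% / 79% | 14% | 63% | 77% |
| 30% | 62% / 69% | 20% | 53% | 73% |
| 40% | 50% / 58% | 24% | 45% | 71% |

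The loss is 80 − 73 = 7 points at 10% unable and 71 − 45 = 26 points at 40%. Retention differs between arms by 4 to 8 points.

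**Check 3: the gain in isolation.** Assume 40% are unable at baseline, 80% of them gain the ability in one arm against 10% in the other, and there is no effect among those already able. A completers-only t-test rejects in about 5% of 4,000 simulated trials, its false-positive rate. A rank test that places gained ability as the best result rejects in about 27%. With 20% unable the figures are about 5% and 9%.

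**The case against.** The strongest reply is about status and reach. These tests are secondary and optional. The primary GRASSP is not described as a completion time: "it evaluates the domains of sensation, strength, quality of different grip patterns and the ability to complete a variety of functional tasks". CAHAI scores 13 items from 1 to 7, and TRI-HFT scores the type of grasp without a time limit. A gain in ability can therefore appear elsewhere. This stands, and it confines the point to the timed tests.

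A reader might infer more than the documents support:

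- *That everyone admitted on wrist movement is unscorable.* The TRI-HFT description recognises passive grasp through positioning of proximal joints, the entry rule joins its conditions with and/or, and no count of wrist-only entrants is given. Some may complete some subcomponents.
- *That one-handed grip removes the grasp measure.* Grasp kinematics use the less affected arm. On the JTT the weaker hand may lack a time, but the stronger hand's times remain.
- *That the plan drops these people.* It is silent. Deletion is the usual behaviour of a repeated-measures ANOVA, and a ceiling score is not excluded. A mixed model would keep the later time, but it would have no baseline from which to observe a change.
- *That finishing more JTT subcomponents would read as worsening.* This needs times to be summed, and no section sums them.
- *That the power loss is much larger.* Completers' log time gives about 47/38/33/27% in the same model. That comparison changes the scale as well as the sample, and the plan names no log transform.
- *That bias must run against an effective arm.* The documents fix neither its direction nor its size.

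Check 2 also favours the speed score, because the effect was generated as a shift in speed. It leaves out the third arm, the follow-ups and the Tukey adjustment.

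**Conclusion.** The point holds for the three timed hand measures and should be fixed before data are seen. It does not threaten the primary outcome. With no value for unable, a participant lacking a baseline time contributes no change to the stated analysis, a move from unable to able is uncredited on these tests, and the analysed set can differ by arm.

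The size is unknown because the documents give no rate of inability. Under the assumptions shown, restricting the analysis to completers costs roughly 7 points of power at 10% unable and 26 points at 40%. These figures illustrate the mechanism and do not predict this trial. That deletion would occur is inferred from the named method, and that some entrants are unable is inferred from the entry rule.

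**What to change.** In STUDY ENDPOINTS, items F, G and J, set a fixed cut-off time for each task before data are seen, and then:

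1. Score the 9HPT as pegs placed per second, with 0 if none is placed by the cut-off.
2. Score each JTT subcomponent and each grasp as 1/time, with 0 if it is not completed by the cut-off.
3. Score the 9HPT and JTT separately by hand and name the hand or hands analysed. Keep grasp on the less affected arm.
4. In Statistical Analysis, analyse all randomised participants who were assessed on these scores. Because the scores have a spike at zero, add a rank-based analysis with unable placed worst as a check.
5. Report seconds descriptively among completers, and the number unable by arm, hand and visit.

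A ceiling time, items completed or censored time would also close the gap. What matters is that one rule is fixed in advance and keeps these people in the analysis.

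The cost is wording in three items and the analysis section, plus a cut-off on the assessment form. No new test, visit or participant is needed. The downside is small: rates are less familiar than seconds, and the spike at zero fits an ANOVA imperfectly.
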